10.2 Overdose

Symptoms of overdose of ASN51 are not yet known. In the case of accidental overdose, subjects should be treated symptomatically as no specific antidote is available.

10.3 Blinding

This is an open-label study.

10.4 Method of assigning subjects to treatment groups

Subjects will be assigned a screening number at the screening visit.

After passing all of the screening assessments, subjects will be allocated to a group according to their availability and the scheduled trial dates.

Subjects will be numbered consecutively, from 1001–1006 (Group 1) or 2001–2006 (Group 2), in the order in which they arrive on the ward and are entered into the trial (ie subjects who will have PET scans during the study will be allocated subject numbers on the day of imaging session 1; all other subjects will be numbered on Day –1).

Replacements for withdrawn subjects will be given a number equal to that of the subject that they replaced plus 100. So, Subject 1001 would be replaced by Subject 1101, and Subject 2004 would be replaced by Subject 2104, and so on.

10.5 Selection and timing of dose for each subject

The treatments to be administered are described in sections 8.1 and 10.1. Subjects will be assigned to treatments as described in section 10.4.

Doses will be given at the same time each day (\pm 15 mins from the dosing time on Day 1).

10.6 Previous and concomitant treatment

Previous treatment restrictions are described in section 9.3.

During the trial, concomitant medication may be given if the subject's GP believes it to be necessary. In addition, up to 2 g paracetamol (acetaminophen) will be allowed

per day for mild analgesia (up to 1 g per dose). Any other concomitant treatment will be given only if deemed strictly necessary by the investigator or co-investigator. In any case, all concomitant treatments will be reported in the CRF along with their daily dosage, duration and reasons for administration. Subjects who have received any concomitant treatment may be withdrawn from the trial at the discretion of an investigator.

10.7 Assessment of compliance

All subjects will be dosed with ASN51 on the research ward under the supervision of 2 suitably trained members of HMR staff. Mouth checks will be done.

Subjects who will have PET scans will be dosed with radiolabelled tracer, [¹⁸F]-IMA601 at Invicro, under the supervision of suitably trained members of staff, at least one of whom will be a registered physician or nurse.

11 Dietary and lifestyle restrictions

Subjects will abide by HMR house rules while on the ward or at Invicro.

Subjects will receive their doses of ASN51 in the fed and fasted states, as follows.

- On Days 1 and 14, subjects will fast (no food or drink other than water) from midnight on the evening before dosing, until 4 h after dosing.
- On Days 2–10, 12, and 13, the study medicine will be given before a standard breakfast.
- On Day 11, subjects will take the study medicine after a high-fat breakfast consisting of 2 fried eggs, 2 strips of bacon, 2 slices of toast and butter, 4 ounces of hash brown potatoes, and a glass of whole milk. Subjects will start the meal approximately 30 min before dosing, and must eat all of it by at least 10 min before dosing.

Other standard meals and drinks will be provided at appropriate times. Because the timings of on-treatment PET scans may change, meals for PET subjects may be provided at unusual times.

Other than the water required to take the study medicine, water will not be allowed for 2 h before and after dosing (Days 1 and 14 only).

No food or drink containing Seville oranges or grapefruit, and no smoking or use of nicotine-containing products, will be allowed from 7 days before the baseline PET scan (PET subjects) or the first dose of trial medication (PBMC subjects) until the end of the study. No alcoholic drinks will be allowed 48 h before the baseline PET scan (PET subjects) or first dose of trial medication (PBMC subjects), until the end of the study. No caffeine- or xanthine-containing products (eg coffee, tea, cola drinks and chocolate) will be allowed from 24 h before: the baseline PET scan (PET subjects) or the first dose of trial medication (PBMC subjects) until discharge from

the ward; imaging session 3 (if applicable, PET subjects); and the follow-up visit (all subjects). Subjects should be advised to avoid eating food containing poppy seeds from screening until the end of the study, because that can cause a positive drugs of abuse test result.

No strenuous exercise will be allowed for 7 days before the baseline PET scan (PET subjects) or the first dose of trial medication (PBMC subjects) until the end of the study.

Subjects must not sunbathe or use a sunbed during the study.

Subjects must use a reliable method of contraception, as follows.

11.1 Contraception requirements

Men

Male subjects must not plan to father a child, or donate sperm, during the trial (from 1 day before the baseline PET scan [PET subjects] or first dose of trial medication [PBMC subjects] until 3 months after their follow-up visit).

Male subjects must not have sex without using a condom, if their partner is a woman of childbearing potential, from 1 day before the baseline PET scan (PET subjects) or first dose of trial medication (PBMC subjects) until 90 days after their last dose of trial medication. Also, their female partners of childbearing potential must use an additional method of contraception (such as an oral contraceptive, cap, or diaphragm [used with spermicide], intrauterine device [IUD], or tubal ligation). Subjects do not need to use any contraception if: they've had a vasectomy, and surgical success has been confirmed by medical assessment, or if their partner is not of childbearing potential. Partners who are not of childbearing potential are defined as: men; post-menopausal women (no menstrual periods for at least 12 months, and FSH at screening confirms post-menopausal status); or women who have no uterus, ovaries, or fallopian tubes.

Subjects who practise true abstinence or who only have same-sex relationships need not use contraception, provided it is in line with their preferred and usual lifestyle (note: periodic abstinence (eg calendar, ovulation, symptothermal, and post-ovulation methods) and withdrawal are not acceptable methods of contraception). Should any such subject stop practising true abstinence, they must use contraception as described above.

Women

Women of non-childbearing potential may take part in the trial as PBMC-only subjects. A woman is considered to be of non-childbearing potential if she meets one of the criteria in inclusion criterion 1.

12 Procedures and observations

Only subjects who meet all the inclusion and no exclusion criteria will be eligible for enrolment into the trial (see section 9). Each subject will be allocated a unique trial number (see section 10.4).

The schedule of procedures is in section 12.1.

Additional timepoints may be introduced, and changes to timepoints may be made, in accordance with section 12.2.

The following assessments will be made.

Pharmacodynamics

Blood samples for PBMC assays will be taken before and frequently during dosing (up to 144 h [6 days] after the last dose). Trough samples will be taken before study drug administration.

Occupancy of O-GlcNAcase by ASN51 will be assessed by PET imaging using the radioligand [¹⁸F]-IMA601 (PET subjects only).

Blood samples will be taken during each PET scan for arterial input function and radio metabolite analysis (PET subjects only).

Safety and tolerability:

Laboratory assessments (routine haematology, clinical chemistry, coagulation, and urinalysis), physical and neurological examinations, 12-lead ECGs, and vital signs (blood pressure, pulse rate, respiratory rate, and tympanic temperature) and C-SSRS will be done frequently until the subject's last visit. AEs will be recorded from screening until the subject's last visit.

Laboratory safety variables to be assessed during the study are in Table 4.

From screening until the follow-up visit, AEs and concomitant medication will be documented as they are reported by the subjects. Subjects will be questioned about AEs on admission to the ward, when procedures are done, and when they return to the ward for outpatient visits/at follow-up.

Pharmacokinetics

Blood samples for assay of ASN51 will be taken before and frequently during dosing (up to 144 h [5 days] after the last dose), and at follow-up. Trough samples will be taken before study drug administration.

PET subjects only: for subjects having imaging session 3 on Day 22 or 23, additional PK samples will be taken approximately 2 h before and after the PET scan.

Other

Structural MRI scans will be done during the screening period (PET subjects only).

12.1 Schedule of procedures

	Screening ¹		Imaging session 1 ²	Treatment period (including imaging session 2 [Day 1], and imaging session 3 [Day 17])							Imaging session 3 ⁴	Follow-up ⁵	
	Visit 1	Visit 2 (MRI)		Day -1	Day 1 ³	Days 2-10	Day 11	Days 12-13	Day 14	Day 17 ⁴			
Informed consent	X												
Inclusion/exclusion criteria	X			X									
Demographics	X												
Medical/surgical history	X												
Allen's test ⁶	X		X		X						X		X
MRI questionnaire ⁷	X	X											
MRI scan ⁷		X											
Admission				X									
Inpatient stay					↔								
Venous cannulation ⁸			X		X					X	X		X
Arterial cannulation ⁹			X		X						X		X
Administration of [¹⁸ F]-IMA601 ¹⁰			X		X						X		X
PET scan ⁶			X		X						X		X
Dose of ASN51 ¹¹					↔								
High-fat breakfast ¹²							X						
Discharge												X	
Outpatient visit													X ⁶
Safety assessments													X
Physical and neurological examination ¹³	X			X									X
FSH test ¹⁴	X												X
Height, weight, and BMI ¹⁵	X	X											
Vital signs ¹⁶	X		X	X	X	X	X	X	X	X	X		X
12-lead ECG ¹⁷	X		X	X	X	X	X	X	X	X	X		X
Serology	X												
Laboratory safety tests ¹⁸	X		X ⁶	X		X ¹⁸			X		X		X
Urine drug screen and cotinine, and alcohol urine test	X			X									

	Screening ¹		Imaging session 1 ²	Treatment period (including imaging session 2 [Day 1], and imaging session 3 [Day 17])								Imaging session 3 ⁴	Follow-up ⁵
	Visit 1	Visit 2 (MRI)		Day -1	Day 1 ³	Days 2–10	Day 11	Days 12–13	Day 14	Day 17 ⁴	Day 20		
C-SSRS	X												X
Blood samples													
PBMC samples ¹⁹					X	X	X	X	X	X	X		
PK plasma samples ²⁰					X	X	X	X	X	X	X	X	X
Arterial blood samples ⁹			X		X					X		X	
Ongoing subject review													
Concomitant medicines	←-----→												
Adverse events	←→												

Abbreviations: BMI: body mass index; C-SSRS: Columbia-Suicide Severity Rating Scale; ECG: electrocardiogram; FSH: follicle stimulating hormone; MRI: magnetic resonance imaging; PBMC: peripheral blood mononuclear cell; PD: pharmacodynamics; PET: positron emission tomography; PK: pharmacokinetics.

Notes:

1. Screening will be within:
 - 28 days before the first dose of trial medication (PBMC-only subjects; see section 8.1.2)
 - 21 days before imaging session 1 (PET subjects only; see section 8.1.3)
2. *PET subjects only* – imaging session 1 (baseline PET scan) will be within 3–7 days before the first dose of trial medication. Subjects will be admitted to the ward the day before their baseline PET scan, and have laboratory safety tests done for inclusion/exclusion criteria before their PET scan.
3. *PET subjects only* – imaging session 2 (on-treatment PET scan) will be at about 5 h postdose on Day 1. Water will not be allowed from 2 h before until 2 h after dosing.
4. *PET subjects only* – imaging session 3 will take place on:
 - Day 17 (3 out of 4 PET subjects per group)
 - Day 22 (1 subject in Group 1)
 - Day 23 (1 subject in Group 2).
5. Follow-up will be:
 - on Day 23 (+ 2 days) (PBMC-only subjects)
 - On Day 23 (+ 2 days) or 2–4 days after imaging session 3, whichever is later (PET subjects).

Additional follow-up owing to SAEs is described in section 12.3.
6. PET subjects only. A sample will be taken for clinical chemistry only.

7. *PET subjects only* – subjects will complete an MRI questionnaire before the MRI scan, to exclude unsuitable subjects. Questionnaires will be done at Screening Visit 1 with the screening physician, and at Screening Visit 2 at Invicro with the radiographer. Screening MRI will be done once all other screening results are available. If a subject is being re-screened (ie missed cohort) and there is already a recent MRI scan available within 3 months from their first screening period (ie if subjects were a reserve subject for a previous group but were not dosed and are no longer within the screening window) they do not need a repeat MRI scan.
8. Subjects will have several cannulas, as below.
 - *All subjects* – on Days 1 and 14, subjects will have a cannula inserted for PK sampling.
 - *PET subjects only* – at each imaging session, subjects will have an additional cannula inserted for administration of the radioligand [¹⁸F]-IMA601.
9. *PET subjects only* – once per imaging session
10. *PET subjects only* – [¹⁸F]-IMA601 administration at the start of each PET scan.
11. Subjects will receive once-daily oral doses of ASN51 on Days 1–14 in the fasted and fed state (fasting requirements and water restrictions are in section 11). Doses will be given at approximately the same time each day (\pm 15 min from dosing time on Day 1).
12. All subjects will be given an FDA high-fat breakfast before dosing on Day 11; see section 11.
13. Full physical and neurological examinations will be done at screening and at the follow-up visit. Brief (symptom-directed) physical examinations will be done at all other timepoints.
14. FSH tests in post-menopausal women (screening only).
15. Weight only at screening visit 2 (MRI; PET subjects only).
16. Vital signs consist of seated systolic and diastolic blood pressure, pulse rate, tympanic temperature, and respiratory rate. Vital signs will be done at the following timepoints.
 - *PBMC-only subjects*: screening; Day -1; predose and at 2, 4, 8, and 12 h postdose on Day 1; before dosing on Days 2–13; before, and at 2, 4, 8, and 12 h after dosing on Day 14; at 24 h (Day 15), 48 h (Day 16), 72 h (Day 17), 96 h (Day 18), 120 h (Day 19), and 144 h (Day 20) after the last dose of ASN51; and at follow-up
 - *PET subjects* will have the same timepoints as PBMC-only subjects, plus additional assessments at: imaging session 1 (baseline) and imaging session 3 (if held on Day 22 or Day 23)TriPLICATE measurements (obtained \geq 5 min apart) will be made at screening. Single measurements will be made at all other timepoints. Measurements should begin with subjects in a seated position, after resting for at least 5 min. Additional unscheduled assessments may be done at the discretion of the investigator. Morning vital signs should always be taken before study drug administration.
17. During the period of residence, ECGs will be recorded at the following timepoints.
 - *PBMC-only subjects*: screening; Day -1; predose and at 2, 4, 8, and 12 h postdose on Day 1; before dosing on Days 2–13; before, and at 2, 4, 8, and 12 h after dosing on Day 14; at 24 h (Day 15), 48 h (Day 16), 72 h (Day 17), 96 h (Day 18), 120 h (Day 19), and 144 h (Day 20) after the last dose of ASN51; and at follow-up
 - *PET subjects* will have the same timepoints as PBMC-only subjects, plus additional assessments at: imaging session 1 (baseline) and imaging session 3 (if held on Day 22 or Day 23)TriPLICATE recordings (obtained \geq 5 min apart) will be made at screening. Single recordings will be done at all other time points. Recordings should be made with subjects in a supine position, after resting for 5 min.

18. Laboratory safety tests consist of haematology, clinical chemistry, coagulation, and urinalysis. Samples are to be taken at screening, Day -1, before dosing on Days 8 and 14, on Day 20, and at follow-up. Samples for clinical chemistry only are to be taken at Imaging session 1.
19. Plasma samples for the PBMC assay will be collected as follows.

PBMC-only subjects

- before and at 4, 8, and 12 h after dosing on Day 1
- before dosing on Day 2
- before and at 4 h after dosing on Day 11
- before and at 4 h, 8 h, and 12 h after dosing on Day 14
- at 24 h (Day 15), 72 h (Day 17), and 144 h (Day 20) after the last dose of ASN51

PET subjects

- before and at 4, and 8 h after dosing on Day 1
- before dosing on Day 2
- 4 h after dosing on Day 11
- before and at 4 h, and 8 h after dosing on Day 14
- at 24 h (Day 15), 72 h (Day 17), and 144 h (Day 20) after the last dose of ASN51

20. Plasma samples for PK assay of ASN51 will be collected at as follows.

PBMC-only subjects

- before and at 0.25, 0.5, 1, 1.5, 2, 3, 4, 6, 8, 12, and 16 h after dosing on Day 1
- before dosing on Days 2, 4, and 7
- before and at 8 h after dosing on Day 11
- before and at 0.25, 0.5, 1, 2, 4, 6, and 12 h after dosing on Day 14
- at 24 h (Day 15), 48 h (Day 16), 96 h (Day 18), and 144 h (Day 20) after the last dose of ASN51; and at follow-up

PET subjects will have the same timepoints as PBMC-only subjects, plus 2 additional samples at imaging session 3 at about 2 h before and 2 h after the PET scan.

Samples scheduled immediately before the PET scan should be taken as close as possible to the planned start of the PET scan. Samples scheduled for the end of the PET scan should be taken as soon as possible after the PET scan is finished. Samples scheduled during the PET scan should be taken either before or after the PET scan, as close to the scheduled timepoint as possible.

When more than one assessment is scheduled at a specific timepoint, PET procedures should be prioritised (if applicable), followed by PK, PBMC, and scheduled safety assessments. Unscheduled safety assessments due to an emergency should always be prioritised. Blood sampling should be done on time. Other procedures should be done as close as possible to the scheduled timepoint.

12.2 Sampling timepoints and additional tests

With the sponsor's approval, additional timepoints may be introduced, and changes to timepoints may be made, if we have reason to believe that the change might improve the quality of the data (for example, if we believe that an important effect of the IMP is occurring at a time when no measurements are scheduled), or if extra procedures are needed in the interest of subject safety. However, the total volume of blood taken in the trial will not exceed the value given in section 12.5.

An additional 48 hours' residence in the ward, and additional outpatient or imaging visits, will be permitted, in the event of a technical failure, to accommodate a later PET scan (detailed further below), and/or if extra observations or samples of blood or urine are needed.

Extra procedures and changes to timepoints which have a significant impact on the scientific value and/or safety of the trial participants will be implemented only after approval of a substantial amendment from the Regulatory Authority (MHRA), unless the changes constitute an urgent safety measure.

With the sponsor's approval, the interval between inpatient and outpatient visits may be changed, if data collected during the trial support the change. The following will **not** be regarded as protocol deviations.

Table 3: Acceptable deviation times

Procedure	Study day	Timepoint	Acceptable deviation
PK and PBMC blood sampling*	Days 1 and 14	Predose	Up to 30 min before dosing
		Up to and including 1 h post dose	± 5 min of the scheduled time
		After 1 h to 4 h post dose	± 10 min of the scheduled time
		After 4 h to 24 h post dose	± 15 min of the scheduled time
	Days 2–13	Predose	Up to 30 min before dosing
	Day 15–20	> 24 h post dose	± 1 h of the scheduled time
	Day 21 onward	Outpatient visits	± 1 day
All other procedures	Days 1 and 14	Predose	Up to 90 min before dosing**
		Up to and including 4 h post dose	± 10 min of the scheduled time
		After 4 h to 24 h post dose	± 15 min of the scheduled time
	Days 2–13	Predose	Before dosing
	Day 15–20	> 24 h post dose	± 1 h of the scheduled time
	Day 21 onward	Outpatient visits	± 1 day

* For subjects having PET scans, samples scheduled immediately before the scan should be taken as close as possible to the planned start of the scan. Samples scheduled for the end of the scan should be taken as soon as possible after the scan is finished. Samples

Procedure	Study day	Timepoint	Acceptable deviation
scheduled during the scan should be taken either before or after the scan, as close to the scheduled timepoint as possible.			
** Samples for urinalysis may be collected anytime from when the subject awakes until the scheduled time.			

PET scans

Timings of on-treatment PET scans may change based on emerging data.

Occasionally, a technical failure, such as unsuccessful radiolabelled tracer synthesis or a PET scanner malfunction, may require a PET scan to be repeated or rescheduled. However, subjects will have no more than 3 PET scans and 3 doses of [¹⁸F]-IMA601 during the study. Therefore, if the failure affects an imaging session before the administration of radioactivity, a scan may be repeated (ideally within about 24 h for on-treatment scans). If the scan is scheduled after a subject has been discharged from the ward, the subjects may be asked to stay at the research unit for up to 24 h longer. Otherwise, the subject may be discharged and later readmitted to the research unit. If a subject can receive no further doses of [¹⁸F]-IMA601, then they may be replaced, on a case-by-case basis, at the discretion of the sponsor.

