- *Imaging session 2.* Subjects will have an on-treatment PET scan at about 5 h postdose on Day 1.
- *Imaging session 3.* Subjects will have an on-treatment PET scan at 3–9 days after their final dose of ASN51:
 - 3 subjects per group on Day 17
 - 1 subject on Day 22 (± 1 day) (Group 1 only)
 - 1 subject on Day 23 (± 1 day) (Group 2 only)

The timing of on-treatment PET scans (imaging sessions 2 and 3) may be altered based on emerging data or study logistical requirements.

Subjects will receive an intravenous (IV) dose of the radiolabelled tracer, [¹⁸F]-IMA601, at the start of each PET scan.

[figure not shown]
Arterial blood sampling will be done during each PET scan to quantify the parent tracer-related radioactivity over the course of the PET scan, and to establish a tracer metabolite-corrected plasma input function. The total arterial blood volume required for each tracer injection will not exceed 120 mL. Arterial cannulation and arterial blood sampling may be reduced or removed if analysis of PET data from previous subjects indicates that non-invasive analysis of the PET scan data can be done. If a non-invasive analysis is not possible, the use of an arterial cannula with each PET scan will continue through the study.

In the case of a technical failure (such as unsuccessful tracer synthesis), subjects may be asked to attend an additional on-treatment imaging session as described in section 12.2. However, no subject will have more than 3 PET scans and 3 doses of [¹⁸F]-IMA601 during the study.

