All subjects

All subjects will receive once-daily doses of ASN51 for 14 days (see section 8.1).

All doses will be given orally, in the fasted or fed state, with about 240 mL of water. Extra water can be given if a subject has trouble swallowing the tablets; that will be recorded in source documents.

Fasting requirements are described in section 11.

PET subjects

PET subjects will also receive IV doses of the radiolabelled tracer [¹⁸F]-IMA601 (non-IMP) on up to 3 occasions (1 at each imaging session).

If one or both on-treatment PET scans need to be rescheduled, eg owing to a technical failure, subjects may have additional imaging sessions. However, subjects will receive no more than 3 doses of [¹⁸F]-IMA601 during the study.

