16.2.7 PET data analyses

Start and end date of each PET scan will be listed together with the scan start/stop time and the Dose drawn up, Dose administered, Residual 1, and Residual 2.

[¹⁸F]-IMA601 regional total volume of distribution (V_T) at each brain scan will be listed for each session and for change from baseline.

The RO values will be listed for imaging sessions 2 and 3, respectively, together with the plasma concentration of ASN51 at the time of the start of each postdose PET scan, which will be calculated by log-linear interpolation from the two closest PK data points by subject and treatment (to be provided by the sponsor).

These concentration data will be transferred to Invicro for the PK-RO analysis. The PK-RO analysis will be provided by Invicro and sent to HMR for the inclusion in the CSR.

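### If imaging session 2 is repeated after the Day 2 dose, no PK sample is scheduled to support it, and the interpolation rule understates the concentration at that scan about 2.1- to 2.4-fold at the implied 48 h half-life

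*Protocol*

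**What the plan says.** **Planned scan.** Protocol section 8.1.3 on imaging session 2: "Subjects will have an on-treatment PET scan at about 5 h postdose on Day 1". It adds: "The timing of on-treatment PET scans (imaging sessions 2 and 3) may be altered based on emerging data or study logistical requirements".

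**Repeat after a failure.** Section 12.2 covers failures such as an unsuccessful tracer synthesis or a scanner fault. If no radioactivity has been given, "a scan may be repeated (ideally within about 24 h for on-treatment scans".

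**Dosing.** Section 10.1: "All subjects will receive once-daily doses of ASN51 for 14 days". Section 10.5 holds each dose to within 15 min of the Day 1 clock time.

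**PK samples.** Section 12.1, note 20, gives Day 1 samples "before and at 0.25, 0.5, 1, 1.5, 2, 3, 4, 6, 8, 12, and 16 h after dosing on Day 1", then "before dosing on Days 2, 4, and 7". PET subjects have the same schedule, "plus 2 additional samples at imaging session 3 at about 2 h before and 2 h after the PET scan". No extra sample is tied to session 2.

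**Concentration at the scan.** Section 16.2.7 lists RO with the ASN51 concentration at the start of each post-dose scan, "which will be calculated by log-linear interpolation from the two closest PK data points by subject and treatment". The values go to the imaging centre for the PK-RO analysis. The PET population (section 16.2.3) needs only a PK result immediately before a scan.

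**Provision for extra samples.** Section 12.2 allows added timepoints with the sponsor's approval. Section 12.5 leaves 30 mL of extra blood for PET subjects.

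**The concern.** Plasma concentration at each post-dose PET scan is a secondary endpoint (section 7.2.2) and the exposure value for the PK-RO analysis. The 16.2.7 rule works at the planned 5 h. It does not require the two PK points to bracket the scan, or to lie in the same dosing interval as the scan.

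The protocol itself provides for a repeat that can fall after the second dose. The last sample before that scan is Day 2 pre-dose and the next is Day 4 pre-dose. The rule then either extends the Day 1 decline past a dose, or draws one line across the Day 2 and Day 3 doses. Both give too low a concentration. Occupancy measured after two doses would be paired with an exposure that leaves out most or all of the second dose, which makes ASN51 look more potent than it is. Section 6.4 says the results will be used to select doses for later patient studies. A sample not taken at the time cannot be recovered.

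**Working it through.** **1. Is any PK sample planned for a repeated session 2?** Count note 20:

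- Day 1: 12 (pre-dose plus 11)
- Days 2, 4 and 7: 3
- Day 11: 2
- Day 14: 8 (pre-dose plus 7)
- 24, 48, 96 and 144 h after the last dose: 4
- Follow-up: 1

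The sum is 12 + 3 + 2 + 8 + 4 + 1 = 30, as in Table 7. Adding the two session 3 samples gives 32, as in Table 8 (32 × 2 mL = 64 mL). Every planned sample is accounted for, and none belongs to a repeated session 2.

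**2. When would the repeat fall?** Planned scan at 5 h, plus 24 h, is 29 h, or 5 h after the Day 2 dose. To come before that dose, the repeat must be done within 24 − 5 = 19 h of the planned scan. The nearest scheduled samples are 16 h, 24 h (Day 2 pre-dose) and 72 h (Day 4 pre-dose).

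**3. Inputs for the size.** Section 6.7 equates 6 days with 3 half-lives, so t½ = 144/3 = 48 h. The PK results are not visible. One-compartment linear PK with equal doses is an assumption, as is absorption (instant, or first-order at 0.5–2 per h). Each dose adds one unit, and k = ln 2/48.

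**4. True value at 29 h, instant absorption.** e^(−29k) + e^(−5k) = 0.658 + 0.930 = 1.588.

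**5. Two readings of the rule.**

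- *Nearest two points (16 h and 24 h).* C(16) = 0.794 and C(24) = 0.707. Extending that line to 29 h gives 0.658. Ratio 1.588/0.658 = 2.41.
- *Bracketing points (24 h and 72 h).* C(72, pre-dose) = 0.354 + 0.500 + 0.707 = 1.561. Interpolation gives 0.707 × (1.561/0.707)^(5/48) = 0.768. Ratio 1.588/0.768 = 2.07.

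**6. Sensitivity at 29 h (true ÷ estimated).** Each range runs from absorption at 0.5 per h to instant.

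| Half-life | 16 h and 24 h points | 24 h and 72 h points |
|---|---|---|
| 24 h | 2.81–3.00 | 2.29–2.45 |
| 36 h | 2.44–2.59 | 2.06–2.18 |
| 48 h | 2.29–2.41 | 1.96–2.07 |
| 60 h | 2.20–2.32 | 1.91–2.00 |
| 72 h | 2.15–2.26 | 1.87–1.96 |

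**7. Scan time (48 h half-life, absorption 1 per h).** A repeat at 8 to 23.5 h, before the second dose, has ratio 1.00. At 25 h the ratio is 1.83–1.89, and at 26 h 2.08–2.22. The planned 5 h scan has 1.00.

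**8. With samples around the repeat (48 h half-life).** Samples at 28 h and 30 h give 1.00–1.01. Samples at 27 h and 31 h give 1.00–1.03.

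**The case against.** The strongest reply is that the remedy is already authorised. Section 12.2 allows added timepoints that might improve data quality, and section 12.5 reserves blood for extra ASN51 assays. A careful site would take a sample, and listed dose and scan times would reveal a dose between sample and scan. This stands so far: a sample is unscheduled, not impossible. But adding it is discretionary and needs sponsor approval within about a day. SAP section 12.1 keeps unscheduled time points out of summaries and analyses. SAP section 3 leaves the PET analysis to the imaging centre, so it is unclear whether that exclusion reaches the interpolation. Even with an added sample, the rule has no same-interval condition.

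SAP sections 6 and 17 also refer to a file note that updated timepoints. It is not visible and might already close the gap.

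A reader might infer more than the documents support:

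- *Every repeat is biased.* It is not. A repeat before the Day 2 dose is bracketed by scheduled samples.
- *The error is simply 2.4-fold.* That needs the nearest-two reading, which is extrapolation although the rule says interpolation. The bracketing reading is equally open and gives 2.1-fold.
- *Moving session 2 to any other treatment day does the same.* It does not. On Day 14 a 5 h scan lies between the 4 h and 6 h samples. In the same model with a 48 h half-life, the ratio is about 1.14 on Day 11 and 1.3–1.5 on Days 4 and 7.
- *The event is likely.* The documents give no scan failure rate. The error also needs a failure before injection, a repeat after the Day 2 dose and no added sample.
- *One such point would dominate the PK-RO fit.* Up to 8 × 2 = 16 post-dose scans are planned and the model is not shown, so its influence cannot be calculated.

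**Conclusion.** The concern holds as a narrow, conditional defect. For a session 2 scan repeated after the Day 2 dose, the stated rule applied to the scheduled samples gives a concentration about 2.1- to 2.4-fold too low. That figure assumes a repeat about 5 h after the dose, one-compartment linear PK, the implied 48 h half-life and fairly fast absorption (1 per h or faster). Over half-lives of 24–72 h and absorption from 0.5 per h to instant, the range is 1.9- to 3.0-fold, always in the same direction. The only value affected is the concentration paired with RO for a subject with such a repeat. The scan's own V_T and RO are untouched, as is any subject scanned as planned. The change is still worth making, because the protocol provides for the contingency, the value is a stated endpoint, and the missing sample cannot be obtained later.

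**What to change.** 1. **Protocol section 12.1 (note 20) and section 12.2.** Make two 2 mL PK samples a scheduled requirement for any on-treatment scan that is moved from its planned time and is not already bracketed by scheduled samples in the same dosing interval. Take one shortly before and one shortly after the scan, both after the most recent ASN51 dose. Because they are scheduled, the SAP's exclusion of unscheduled data would not apply.
2. **Protocol section 16.2.7.** Replace the two-closest-points rule with the two PK samples that bracket the scan start with no ASN51 dose between them. Record the number of doses received before each scan.
3. **File note.** Check whether it already covers PK sampling around a rescheduled session 2, and align it with the protocol text.

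The cost is 2 × 2 mL = 4 mL of the 30 mL allowance, only in a subject whose scan is moved, plus short text changes. Under the model above, the error at a 29 h scan falls to 1.00–1.03-fold.
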